5.4.4 Secondary Feasibility Endpoints

The secondary feasibility endpoint(s) include:

Proportion of subjects that achieve long-term technical success. Long-term technical success is defined as electrical isolation of the pulmonary veins and posterior left atrium assessed at a follow-up electro-anatomical remapping procedure performed 3-months post index procedure.

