5.13.3 Pre-Discharge

Prior to hospital discharge the following data will be collected:

- Use, changes in or discontinuation of anticoagulation, rate control and/or antiarrhythmic medications;
- Cardioversion(s) since surgery;
- For subjects on warfarin, assessment of INR therapeutic levels (maintain as clinically indicated);
- For subjects on dabigatran, perform a PTT and, if required, a thrombin time (Section 4.7.2.7 Anticoagulation Regimen);

- Cardiac rhythm as determined by a 12-lead ECG on day of hospital discharge;
- Heart failure status as assessed by NYHA classification on day of hospital discharge; and Adverse Events.

5.13.4 1 Month Follow-Up

Discharged subjects will return for an office visit 30 days (± 7 days) postablation treatment. Subjects that continue to be hospitalized 30 days postablation will have their 30-Day Follow-Up assessment performed at discharge. At a minimum, the following data will be collected at 30 Day Follow-Up visit:

- Use, changes in or discontinuation of anticoagulation, rate control and/or antiarrhythmic medications;
- Cardioversions since last visit;
- For subjects on anticoagulants, assessment of INR/PTT therapeutic levels (maintain as clinically indicated):
- Cardiac rhythm as determined by a 12-lead ECG at the time of the visit;
- Heart failure status as assessed by NYHA classification at the time of visit;
- Any hospital readmissions, including admission and discharge dates, since discharge from the original procedure; and

5.13.5 3 Month Follow-Up

Subjects will return for an office visit at the end of the blanking period (90 days \pm 14 days post-ablation treatment). During the blanking period, any recurrence of AF will be documented; however, recurrences of AF, AFL or AT during this time will not be considered therapeutic treatment failures. Subjects are not permitted to undergo repeat ablation during the blanking period. If a repeat ablation procedure is performed during this time, the subjects will be considered a therapeutic treatment failure and exited from the study.

At a minimum, the following data will be collected at the end of the blanking period follow-up visit:

- Use, changes in or discontinuation of anticoagulation, rate control and/or antiarrhythmic medications;
- Cardioversions since last visit;
- Any additional ablation procedures performed;
- For subjects on anticoagulants, assessment of INR/PTT therapeutic levels (maintain as clinically indicated);

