7.1 General Statistical Considerations

The primary objective of this study is to characterize the safety and feasibility of the FARAPULSE Cardiac Ablation System in subjects with paroxysmal atrial fibrillation undergoing cardiac surgery.

The study is a feasibility study with no formal hypothesis testing and therefore no required sample size. Study results will be presented using descriptive statistics. Results from this study will be used to design additional clinical studies.

All subjects will be followed on an intent-to-treat basis. The device performance will be assessed based on a per-protocol analysis of the primary safety and feasibility endpoints and secondary efficacy endpoints. An intent-to-treat analysis, along with other secondary analyses, will also be completed and reported.

Demographic, baseline clinical and disease characteristics, procedural results and primary, secondary and all additional endpoints will be summarized using descriptive statistics.

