7.4 Imputation for Missing Data

Imputations for missing data in (e.g., withdrawn subjects, loss to follow-up, missing data) will not be performed. Analyses will be performed with all available data only.

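### Exiting subjects re-ablated in the blanking period contradicts the intent-to-treat follow-up in 7.1, loses later SAE data and may inflate the 3-month remap success rate

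*Combined protocol and SAP*

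**What the plan says.** Section 5.13.5 (3 Month Follow-Up) first prohibits the procedure: "Subjects are not permitted to undergo repeat ablation during the blanking period". It then provides for the case where it happens anyway: "the subjects will be considered a therapeutic treatment failure and exited from the study".

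Section 7.1 sets the follow-up principle: "All subjects will be followed on an intent-to-treat basis". On analysis sets it says: "The device performance will be assessed based on a per-protocol analysis of the primary safety and feasibility endpoints and secondary efficacy endpoints". It adds: "An intent-to-treat analysis, along with other secondary analyses, will also be completed and reported". The per-protocol set is not defined.

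Long-term technical success (5.4.4, repeated in 7.6.2) is "electrical isolation of the pulmonary veins and posterior left atrium assessed at a follow-up electro-anatomical remapping procedure performed 3-months post index procedure". Section 7.4 says: "Imputations for missing data in (e.g., withdrawn subjects, loss to follow-up, missing data) will not be performed", and "Analyses will be performed with all available data only".

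Section 5.4.5 counts a repeat ablation at any time up to Month 12 as a therapeutic failure and says nothing of exit. The Month 3, 6 and 12 visits (5.13.5 to 5.13.7) each record further ablation procedures. Section 5.13.5 also lets the investigator close gaps found at the 3-month remap.

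**The concern.** The exit rule joins two separate things: scoring a subject as a therapeutic failure, and stopping data collection on that subject. Only the first is needed for the therapeutic success result. The second conflicts with 7.1 and removes data that other endpoints need.

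The loss is probably informative. Section 6.1.1 ties further ablation to an ineffective study ablation with recurrent atrial fibrillation, so subjects re-ablated early are likely to be those whose lesion did not hold. That is an inference, but a reasonable one. If they leave before the remap, the subjects who remain are a favourable selection for the durability endpoint.

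Safety follow-up suffers as well. The only post-ablation CT or MRI in Table 4, the planned check on pulmonary vein patency, is at Month 3. The phrenic component of the primary safety composite needs status at 12 months, and the secondary safety endpoint runs over four intervals to Month 12. This is a first-in-man study of at most 25 subjects whose results will inform later trials, and one subject is 1/25 = 4% of the sample.

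**Working it through.** The plan gives no rate of early re-ablation, no assumed success rate and no hypothesis test, so there is no figure to reproduce. The check compares the sections and then illustrates the size.

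**1. Is the exit needed for scoring?** No. Section 5.4.5 already makes the subject a failure without it. The Month 3 visit also asks about additional ablations. Since the preceding visit is at Day 30, many such procedures would fall in the blanking period, and 5.13.5 would already have exited those subjects.

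**2. Does any section keep an exited subject in the visits?** None does. The only continuing follow-up is event-specific: 5.10 and 8.2 follow an adverse event already open until it resolves or is stable. No section says how exited subjects count in the remap, phrenic or SAE denominators.

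**3. What is lost, by timing of the repeat ablation (SAE intervals from 5.4.2)?**

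| Repeat ablation | Procedure to Day 30 | Day 30 to Month 3 | Month 3 to 6 | Month 6 to 12 |
|---|---|---|---|---|
| Before the Day 30 visit | truncated | lost | lost | lost |
| Between Day 30 and the Month 3 visit | complete | truncated | lost | lost |

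In both rows, the remap and the 3-month CT/MRI are lost if the repeat ablation comes before them.

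**4. Effect on long-term technical success.** Assume 25 treated, *s* isolated at the remap, and *k* non-isolated subjects exited before it. The available-data rate is *s*/(25 − *k*). Counting exits as not achieving success gives *s*/25.

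| *k* | *s* = 18, available data | *s* = 18, all 25 | *s* = 20, available data | *s* = 20, all 25 |
|---|---|---|---|---|
| 1 | 18/24 = 75.0% | 72.0% | 20/24 = 83.3% | 80.0% |
| 2 | 18/23 = 78.3% | 72.0% | 20/23 = 87.0% | 80.0% |

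The first exit adds 3.0 points (75.0 − 72.0) or 3.3 points (83.3 − 80.0). Two exits add 6.3 (78.3 − 72.0) or 7.0 (87.0 − 80.0). The values of *s* and *k* are assumptions.

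**5. Effect on safety proportions.** For a 12-month component with no observed event and two exits, the report would be 0/23 (exact 95% upper limit 14.8%). The data would allow anything from 0/25 to 2/25 = 8.0%. For an SAE interval that both exited subjects miss entirely, with three subjects observed to have an SAE, the report would be 3/23 = 13.0%. The possible values run from 3/25 = 12.0% to 5/25 = 20.0%.

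**6. Overlap with the remap.** The Month 3 window is 90 ± 14 days, so it opens at 90 − 14 = day 76, inside the blanking period. A gap closure at a remap on, say, day 80 is allowed by one part of 5.13.5. Read literally, it is also a prohibited repeat ablation under another part and triggers failure and exit. The remap result would then exist, but Months 3 to 12 would be lost.

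**The case against.** The strongest case against is that few subjects will be affected. Repeat ablation in blanking is prohibited, recurrences in that period are not scored as failures, and a remap with optional gap closure is already scheduled at 3 months. The study is descriptive. All of this stands, and it is why the figures are illustrative. But the protocol wrote a rule for the case, so it was foreseen, and the day-76 overlap gives a second route to exit.

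The main device-performance analysis is per-protocol. That set might exclude these subjects whether or not they are exited, so the fix may leave that analysis unchanged. This also stands. The harm is clearest in the promised ITT analysis.

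The endpoint text gives no denominator, so an ITT analysis could count a subject without demonstrated isolation as not achieving success. That is possible but unstated, and the available-data rule in 7.4 points the other way. A reader might infer that the rate is certainly biased upward; the documents support only that it may be.

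A reader might also infer that exit ends all data collection and that a related phrenic paralysis would never be recorded. Sections 5.10 and 8.2 do not support this, because a paralysis already open as an adverse event should still be followed. That follow-up may, however, stop at stability before 12 months, and the 12-month fluoroscopy in Table 4 is only as needed. Most other components of the primary safety composite use a window of 30 days or discharge, so a later re-ablation would usually leave them complete.

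**Conclusion.** The point holds in this limited form. The exit rule in 5.13.5 contradicts the follow-up stated in 7.1 and serves no scoring purpose. It removes later SAE collection: one interval truncated and two lost for re-ablation between Day 30 and Month 3, or one truncated and three lost for earlier re-ablation. If re-ablation precedes the remap, it also removes the remap and the 3-month CT/MRI and may raise the reported technical success rate, by about 3 points for one exit and 6 to 7 for two under the assumed counts.

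This rests on three assumptions: that exit means no further study visits, that 7.4 governs the remap denominator, and that subjects re-ablated early are mostly lesion failures. Therapeutic success is not affected, since these subjects are scored as failures in any case. It would go too far to call the blanking boundary arbitrary, because it is prespecified. The defect is that crossing it ends follow-up.

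**What to change.** - In 5.13.5, delete the closing words that exit the subject. State that the subject is scored a therapeutic failure and remains in all scheduled data collection to Month 12, with SAEs after the repeat ablation flagged.
- In 7.6.2, state that a subject re-ablated before the remap counts as not achieving long-term technical success in the ITT analysis, and report the available-data rate beside it. Any map taken at the repeat procedure should be descriptive only, since isolation at an earlier date does not show isolation at 3 months.
- Reconcile the blanking-period rule with the gap closure allowed at a remap whose window opens at day 76. The sponsor needs to say how such a closure is classified.

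The cost is one deleted clause and a few added sentences. The visits are already in the schedule and few subjects should be involved. The technical success rate may come out slightly less favourable.

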Understanding the need for creating electrical isolation of the pulmonary veins, treatment paradigms have focused on creating circumferential lesions or wide circumferential lesion sets that block electrical continuity between the pulmonary veins and the left atrium. In a wide circumferential ablation (WACA) procedure, operators must form a contiguous line of electrical block around ipsilateral pulmonary veins using fluoroscopic guidance and electroanatomical mapping technologies. A limited assessment of lesion formation and position is determined by monitoring voltage reduction of the local electrogram at the target site. Electrical gaps in lesion sets occur frequently, leading to recurrent AF and/or creation of substrate susceptible to reentrant atrial tachycardias.**xii Ablation technologies that rely upon indirect assessment of lesion formation are challenged to deliver improved durability and therefore long-term efficacy of therapy.

3.2 Surgical Ablation:

The Maze Procedure involves open heart surgery on cardiopulmonary bypass. Areas of cardiac tissue are isolated, either by cut and sew methods or electrosurgically, creating a "maze" which prevents propagation of ectopic AF impulses^{xxiii, xxiii} notes: "While few patients are candidates for a stand-alone surgical procedure to cure AF using the maze or LA ablation techniques, these approaches can be an effective adjunct to coronary bypass or valve repair surgery to prevent recurrent postoperative AF."

Reported failure rates for the maze procedure are as high as 30%. Jais 2002 summarized the conclusions from surgical treatments for AF.xxiv

- reduction of the atrial tissue mass available for fibrillation is effective in preventing maintenance of AF;
- the left atrium plays a dominant role in maintenance and initiation of AF;
- limited lesions placed around pulmonary veins can be as effective as complex ablation schema (maze)and safer.

However, Wisser 2007 reported results of a small non-randomized study comparing two groups of patients, all treated surgically for permanent AF at the same time as other major heart surgery. Group 1 (N=29) received a classic maze procedure: freedom from AF at 19 months follow up was 86%. Group 2 (N=43) received epicardial pulmonary vein isolation treatment, and freedom from AF at follow up was 59%. This difference was statistically significant.

3.3 Irreversible Electroporation (IRE):

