5.13.1 Baseline

The following baseline data will be collected:

- Medical history
- Medication history
- Pregnancy test (if applicable)
- 12-lead ECG
- Cardiac CT or MRI
- NYHA Classification
- TEE or other imaging modality for exclusion of left atrial thrombus

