- Cardiac rhythm as determined by a 12-lead ECG at the time of the visit;
- Heart failure status as assessed by NYHA classification at the time of visit;
- Any hospital readmissions, including admission and discharge dates, since the previous visit; and
- Adverse events.
- If a subject is symptomatic for AF at the end of the blanking period, an event monitor will be provided to be used up to the 6-month follow-up visit to capture AF episodes.
- Patients will undergo an electro-anatomical remapping procedure to assess electrical isolation of the posterior left atrium and pulmonary veins. Any electrical gaps may be closed at the investigator's discretion using a commercially approved ablation device. This will consist of placement of catheters in the left atrium via femoral access and transeptal puncture using conventional electrophysiology techniques.
- Patients will undergo a cardiac CT or MRI scan at 3 months to assess the patency of the pulmonary veins.

5.13.6 6 Month Follow-up

Subjects will return for an office visit 6 months (180 days \pm 30 days) postablation treatment. At a minimum, the following data will be collected at 6 months:

- Use, changes in or discontinuation of anticoagulation, rate control and/or antiarrhythmic medications;
- Cardioversions since last visit;
- · Any additional ablation procedures performed;
- For subjects on anticoagulants, assessment of INR/PTT therapeutic levels (maintain as clinically indicated);
- Cardiac rhythm as determined by a 12-lead ECG at the time of the visit;
- Heart failure status as assessed by NYHA classification at the time of visit;
- Cardiac rhythm as determined by a 24-hour continuous ECG monitor following the visit for subjects in NSR at the time of the visit;
- Any hospital readmissions, including admission and discharge dates, since the previous visit; and
- Adverse events.

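### The only scheduled vein-patency scan after the index procedure shares a window with a remap at which another device may be used, and no order is set, so a narrowing may not be attributable to the study device

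*Combined protocol and SAP*

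**What the plan says.** Section 5.13.5 opens: "Subjects will return for an office visit at the end of the blanking period", with a window of 90 ± 14 days. Among that visit's assessments it lists, in this order:

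- The remap: "Patients will undergo an electro-anatomical remapping procedure to assess electrical isolation of the posterior left atrium and pulmonary veins". At it, "Any electrical gaps may be closed at the investigator's discretion using a commercially approved ablation device".
- The scan: "Patients will undergo a cardiac CT or MRI scan at 3 months to assess the patency of the pulmonary veins".

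Table 4 marks both in the 3-month column. It marks the CT or MRI row at baseline and at 3 months only, and Section 5.13.1 lists "Cardiac CT or MRI" among the baseline data.

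Sections 5.4.1 and 7.7.1 make severe pulmonary vein stenosis a component of the primary safety composite. An event counts if it is related to the investigational procedure or device and falls within 30 days of the ablation or hospital discharge, whichever is later, except as noted in the list. Phrenic nerve paralysis carries its own 12-month time point there; stenosis carries none. Section 7.7.1 has adverse events adjudicated for device and procedure relatedness, and Section 10.12 assigns adjudication to the Clinical Events Committee.

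On left atrial thrombus, Section 5.13.1 lists at baseline "TEE or other imaging modality for exclusion of left atrial thrombus", and the objective imaging row of Table 4 is marked at baseline only. The 3-month remap involves "placement of catheters in the left atrium via femoral access and transeptal puncture using conventional electrophysiology techniques"; Section 5.13.5 does not mention a thrombus check.

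**The concern.** The 3-month scan is the only scheduled look at the veins after study-device ablation. Followed exactly, the plan allows that look to come after a second ablation device has been used on the same veins.

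A narrowing found then has two candidate causes. The baseline scan shows that it is new since surgery but not which device produced it. Adjudicators can weigh the case, but they cannot recover an image from before gap closure that nobody was required to take. In a descriptive first-in-man study of up to 25 subjects, one or two such cases would be a visible part of the safety result.

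**Working it through.** The plan states no figure on this point, so there is none to reproduce. The check sets the passages side by side and adds simple arithmetic.

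**1. Window.** From Section 5.13.5 and Table 4: 90 − 14 = day 76 and 90 + 14 = day 104, which is 104 − 76 + 1 = 29 days. The scan may therefore precede or follow the remap by up to 28 days.

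**2. Order.** Section 5.13.5, Table 4 and the mapping text in Section 5.13.7.2 state none. The remap is listed before the scan, but a list order is not a sequence rule.

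**3. What each result can show.**

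| Scan relative to gap closure | No narrowing seen | Narrowing seen |
|---|---|---|
| Before, or no closure done | Supports absence of stenosis | No second device has been used |
| After closure at or near a vein | Still supports absence of stenosis: neither device left a visible narrowing | Study device or second device; not separable |
| After closure elsewhere in the posterior left atrium | Supports absence of stenosis | Second device was not used at the vein |

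Only one cell is a problem: a positive scan after closure at or near a vein.

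**4. Size when that cell occurs.** The sample size is up to 25 (Section 5.5). If 25 are scanned and one such narrowing is seen, the study-device count is either 0/25 = 0% or 1/25 = 4%, depending on attribution. Each further case widens the range by another 4 points.

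**5. Size when it does not occur.** With no narrowing in 25 scans, the exact one-sided 95% upper bound is 1 − 0.05^(1/25) = 11.3%, whatever the order of scan and remap.

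**6. Link to the primary endpoint.** The scan falls 76 − 30 = 46 to 104 − 30 = 74 days after the 30-day limit. Unless discharge is very late, a stenosis first seen on it lies outside the composite's written window, whichever assessment comes first. Yet stenosis is listed as a component, and no earlier scan is scheduled. These passages do not fit together.

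**7. Thrombus check.** The plan schedules it before one left atrial entry and is silent on the next. That is a gap in the text, not a contradiction.

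**The case against.** The strongest reply is that little is lost. Further ablation does not widen a vein, so a clean scan after closure is as reassuring as one before it, and any misattribution of a positive scan runs against the study device. Additional ablation procedures are recorded at the 3-month visit, a baseline scan exists, and the committee sees source documents. All of this stands, and it confines the problem to positive scans. It does not remove it: no pre-closure image is guaranteed, and no rule says how such a case is counted.

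Four stronger readings are tempting and are not supported.

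- *A scan after closure says nothing about stenosis.* A reader might then discard such scans, so that with 5 of 25 removed the zero-event bound rises from 11.3% to 1 − 0.05^(1/20) = 13.9%. Clean scans should not be discarded, so this loss is not real.
- *About half the scans follow the remap, affecting 1 to 6 subjects.* With independent, uniform dates, (1 − 1/29)/2 = 0.483, about 12 of 25; multiplying by closure rates of 10% to 50% gives 1.2 to 6.0. The documents support neither the date model nor the rates, and the product treats every closure as being at a vein. The background statement "Electrical gaps in lesion sets occur frequently" concerns wide circumferential catheter ablation, not this device. Also, 25 is a ceiling: subjects count as enrolled at consent (Section 5.9), so fewer may reach the scan.
- *The primary endpoint is compromised.* The composite's 30-day or discharge window leaves the scan's role in it unclear in either order.
- *The plan contradicts itself on thrombus.* The follow-up list is a minimum, the remap is to use conventional technique, and the workflow documents cited in Section 5.13.2 are not available here. Sites may well check by local practice.

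**Conclusion.** The point holds in a limited form. The plan lets its only scheduled post-index vein-patency scan follow ablation with another device, and a narrowing seen after closure at or near a vein then cannot be attributed to the study device. Clean scans keep their value.

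How many subjects would be affected is unknown. It depends on the gap-closure rate, on how often closure is at or near a vein, on the order sites choose, and on how often narrowing occurs; the documents give none of these. Each case shifts the study-device proportion by 4 percentage points if 25 are scanned, and by more if fewer are. The change is worth making because it is cheap and because an image not taken before closure cannot be obtained afterwards.

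Two matters need reconciling alongside it: the stenosis component's time window against its 3-month scan, and whether the baseline thrombus check extends to the 3-month entry.

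**What to change.** - **Order.** State in Section 5.13.5, and in a footnote to Table 4, that the 3-month CT or MRI for vein patency is obtained before the remap, within the same 90 ± 14 day window.
- **Data.** Record the dates of the scan and the remap. Flag any scan done after gap closure.
- **Reporting.** Report vein findings from flagged scans separately from those attributable to the study device. Keep clean scans of either kind in the denominator.
- **Endpoint window.** Reconcile the 30-day or discharge window in Sections 5.4.1 and 7.7.1 with a stenosis assessment that first takes place at 3 months.
- **Thrombus check.** Reconcile Sections 5.13.1 and 5.13.5 and Table 4 on whether the baseline check applies to the 3-month left atrial entry. The clinical rule is for the sponsor and investigators to set.

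Cost of the first three items: a sentence, a footnote, two dates and a flag on the CRF, and one extra line in the safety table. No procedure is added, since scan and remap are already scheduled. The downside is a scheduling constraint: both must fit, in order, within 29 days, and some subjects will miss it. The flag covers any of those scanned after closure.
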